In recent years, AI techniques—particularly deep learning (DL) methods—have advanced rapidly, achieving diagnostic accuracy comparable to human experts in many medical image analysis tasks with high efficiency. Examples include multi-organ segmentation in CT data, lesion segmentation in dental scans, retinal vessel segmentation in fundus images, and disease classification based on pathological images. Several studies have already applied DL methods to the diagnosis and severity prediction of acute respiratory distress syndrome (ARDS), demonstrating preliminary progress [27, 28]. AI can automatically and effectively analyze and segment acutely injured lungs, predict the development of ARDS, assess alveolar recruitment, and

quantify relationships between lung tissue characteristics and clinical outcomes. The application of these technologies is expected to assist healthcare professionals in delivering better patient care, thereby reducing the disease burden.

However, two limitations persist in current approaches. First, existing methods lack the ability to process multimodal data. Models are typically restricted to partial datasets, using machine learning techniques such as logistic regression, support vector machines, or random forests for textual data—including age, sex, and T-cell counts—while employing a separate deep learning model for CT imaging analysis. This fragmented view of patient information compromises predictive accuracy in certain cases. Second, current methods fail to balance performance with interpretability. Although deep learning models such as convolutional neural networks (CNNs) may outperform traditional machine learning approaches like multivariable Cox regression in predictive accuracy, they often lack transparency in their decision-making process. Model interpretability is crucial in clinical settings, as physicians need to understand the factors influencing predictions to avoid unexpected errors when incorporating AI-based recommendations.

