2. Admission to the **Intensive Care Unit (ICU) for more than 48 hours**.
3. Availability of **chest CT imaging data**.

Exclusion Criteria

1. Patients aged <18 years.
2. Patients with incomplete medical records.
3. Absence of chest CT imaging or presence of technically inadequate/uninterpretable chest CT images.

Sample Size and Data Partitioning

This study is designed as a multicenter, large-sample, retrospective observational study and plans to include a total of 400 patients with ARDS who meet the eligibility criteria. Of these, 300 cases will be contributed by the primary institution and Sub-center 1, and 100 cases by Sub-center 2.

The study does not involve conventional experimental or control groups. Instead, cases will be partitioned into three datasets according to the model development workflow:

Training set: 276 cases (approximately 80% of the combined cases from the primary institution and Sub-center 2), obtained through stratified random sampling to preserve the distribution of mild, moderate, and severe ARDS;

Internal validation set: 69 cases (approximately 20% of cases from the same two centers), used to monitor overfitting and optimize model hyperparameters;

External test set: 55 cases, all derived from Sub-center 1 and entirely independent of the model development process, used to evaluate model generalizability.

Primary Outcome Measures

The primary outcomes of this study focus on the overall effectiveness of the proposed AI-based framework across three key clinical tasks:

(1) Accuracy of ARDS severity classification, defined as the agreement between model-predicted ARDS severity (mild, moderate, or severe) and the reference clinical classification based on the 2023 global ARDS criteria, assessed using chest CT images obtained within 24 hours of ICU admission;

(2) Treatment plan matching rate, defined as concordance between model-recommended and actual clinical management across five intervention modalities (mechanical ventilation, high-flow oxygen therapy, non-invasive ventilation, prone positioning, and neuromuscular blockade), evaluated at the time of index chest CT acquisition;

(3) Accuracy of 28-day in-hospital mortality prediction, defined as the ability of the model to predict all-cause in-hospital mortality within 28 days of ICU admission.

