These three outcomes collectively reflect the overall effectiveness of the model within a closed-loop framework encompassing disease stratification, treatment recommendation, and prognosis prediction.

Secondary Outcome Measures

Secondary outcomes include comparative performance improvement of the proposed model over commonly used baseline AI models; calibration performance of mortality prediction; interpretability analyses based on imaging-derived and clinical feature contributions; and assessment of the association between treatment concordance and 28-day in-hospital mortality using multivariable regression models.

Research procedures

1. Data collection

(1) Demographic and Baseline Clinical Data

Age, sex, body mass index (BMI), comorbidities (including chronic kidney disease, coronary artery disease, hypertension, diabetes, liver cirrhosis, HIV infection, etc.), primary etiology of ARDS, and receipt of mechanical ventilation, high-flow nasal oxygen therapy, or ECMO. BMI is calculated as weight (kg) divided by height squared (m^2).

(2) Physiologic Parameters

Body temperature (T), heart rate (HR), respiratory rate (RR), peripheral oxygen saturation (SpO_2), and mean arterial pressure (MAP).

(3) Laboratory Parameters

pH, partial pressure of arterial oxygen (PaO_2), fraction of inspired oxygen (FiO_2), partial pressure of arterial carbon dioxide (PCO_2), lactate (Lac), platelet count (PLT), white blood cell count (WBC), hemoglobin (Hb), serum creatinine, C-reactive protein (CRP), procalcitonin (PCT), international normalized ratio (INR), B-type natriuretic peptide (BNP), and interleukin-6 (IL-6).

(4) Ventilator or High-Flow Oxygen Parameters

Positive end-expiratory pressure (PEEP), tidal volume (TV), plateau pressure (Pplat), and flow rate (FLOW).

(5) Other Clinical Scores

Sequential Organ Failure Assessment (SOFA) score and Acute Physiology and Chronic Health Evaluation II (APACHE II) score.

2. CT Equipment and Scanning Parameters

Chest CT images included in this study were acquired from two CT scanners with the following parameters:

CT1 (64-slice): Manufacturer: Philips; Model: Brilliance; Tube voltage: 120 kV; Tube current: 1000 mA; Slice thickness: 5 mm; Slice interval: 5 mm; Pitch: 0.789:1.

CT2 (128-slice): Manufacturer: United Imaging; Model: uCTR760; Tube voltage: 120 kV; Tube current: 1000 mA; Slice thickness: 5 mm; Slice interval: 5 mm; Pitch: 0.984:1.

3. Quantitative Assessment of ARDS

Preliminary Image Processing

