The sample size was preliminarily estimated using the event-per-variable principle. The mortality prediction component is designed to include no more than 15 candidate predictors in the final multivariable logistic regression model. Following the commonly accepted criterion of at least 10 outcome events per predictor, a minimum of 150 death

events is required to ensure model stability and interpretability. Based on historical data from the participating centers, the in-ICU mortality rate among patients with ARDS is approximately 37.5%. Accordingly, the total target sample size for this study is estimated to be approximately 400 patients.

Statistical Analysis Plan

All eligible cases will be stratified and randomly sampled at an 8:2 ratio within Shanghai General Hospital and its affiliated centers to form the model training set and internal validation set. Cases from an additional participating center will be reserved as an independent external test cohort.

Model performance will be evaluated for three predefined tasks: ARDS severity classification, treatment strategy prediction, and mortality risk prediction. Performance metrics will include accuracy, balanced accuracy, area under the receiver operating characteristic curve (AUC), precision–recall curve analysis, and the Brier score. During model development, five independent repeated experiments will be conducted, and performance will be reported as mean values with standard deviations.

For comparative performance assessment, results from the five independent experiments will be compared using two-sided Wilcoxon rank-sum tests, with a significance threshold of 0.05. Different levels of statistical significance will be denoted using conventional symbols (e.g., “*”, “**”) corresponding to predefined P-value ranges.

To assess the association between model outputs and clinical outcomes, model-recommended intervention sets will first be encoded for agreement with actual clinical management. These agreement variables will then be incorporated into multivariable logistic regression models together with six imaging-derived anatomical features (e.g., diaphragmatic height, lung volume). Adjusted odds ratios with 95% confidence intervals will be reported, and a two-sided P value <0.05 will be considered statistically significant.

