For mortality risk prediction, ARDS severity classification and treatment strategy information will be sequentially added to the input features to evaluate their incremental impact on balanced accuracy and Brier score. Model calibration and discrimination will be assessed using calibration curves and precision–recall curves. In addition, least absolute shrinkage and selection operator (LASSO) regression will be applied to all structural, pathological, and intervention-related variables, and standardized coefficients will be extracted to facilitate interpretation of key risk-driving factors across different ARDS severity strata.

Ethics and Informed Consent

This study is a multicenter, retrospective, observational study involving the secondary use of previously collected clinical and imaging data. The study protocol, informed consent materials (where applicable), and all subject-related documents were submitted to the institutional ethics committee and approved prior to study initiation. The study will be conducted in accordance with the Declaration of Helsinki and relevant national and institutional regulations.

The investigators will submit periodic progress reports to the ethics committee as required. Any protocol amendments or changes related to informed consent procedures will be reported to and approved by the ethics committee before implementation, unless such changes are necessary to eliminate an immediate and direct risk to participants, in which case the ethics committee will be notified promptly. The ethics committee will also be informed in writing upon study suspension or completion.

Given the retrospective nature of the study and the use of existing identifiable data without commercial interest, a partial waiver of informed consent was approved by the ethics committee. For participants who can be successfully contacted, investigators will first provide oral information about the study and document the communication. If participants or their legal representatives subsequently return for clinical follow-up, written informed consent will be obtained. For participants who cannot be contacted, the requirement for informed consent is waived in accordance with ethical and regulatory guidelines.

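### For 28-day mortality the plan commits only to unnamed AI baselines, so it would give no estimate of what the model adds to the severity scores and oxygenation data already collected

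*Combined protocol and SAP*

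**What the plan says.** - **Mortality outcome.** Primary Outcome Measures, item 3, is defined as "the ability of the model to predict all-cause in-hospital mortality within 28 days of ICU admission". It names no reference predictor.
- **Comparator.** Secondary Outcome Measures lists "comparative performance improvement of the proposed model over commonly used baseline AI models". Neither that section nor the Statistical Analysis Plan says which baselines these are or what inputs they receive.
- **Test.** Under the Statistical Analysis Plan, "results from the five independent experiments will be compared using two-sided Wilcoxon rank-sum tests, with a significance threshold of 0.05".
- **Bedside data.** Data collection item 5 lists "Sequential Organ Failure Assessment (SOFA) score and Acute Physiology and Chronic Health Evaluation II (APACHE II) score", and item 3 lists PaO2 and FiO2. The two scores are not mentioned again in the outcomes or the Statistical Analysis Plan.
- **Clinical severity class.** In primary outcome 1 this is the reference standard: the model is scored by agreement with the "reference clinical classification based on the 2023 global ARDS criteria".
- **Nearest added-value analysis.** For mortality, the Statistical Analysis Plan states that "ARDS severity classification and treatment strategy information will be sequentially added to the input features to evaluate their incremental impact on balanced accuracy and Brier" (the last word refers to the Brier score).

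**The concern.** The Introduction and Primary Objective aim at risk stratification and a tool for clinical use. A clinician deciding whether to use such a tool already has a blood gas and, in this dataset, SOFA and APACHE II. The useful question is how much better 28-day death is predicted with the CT model than with that information alone. A gain over other AI models does not answer it, because nothing shows how those baselines compare with the scores.

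Without the comparison, the report could show that the model outperforms its AI baselines and still leave the reader unable to tell whether it adds anything to APACHE II or the PaO2/FiO2 class. The data to answer this will be in hand, so only the analysis is missing.

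**Working it through.** **1. Does any planned analysis supply the estimate?**

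| Planned analysis | What it answers | Added value over bedside data? |
|---|---|---|
| Comparison with AI baselines | Proposed model versus unnamed AI models | No bedside comparator committed to |
| Sequential addition of severity and treatment information | What severity adds to the model | Reverse question. It does not say whether the class is clinical or model-predicted, and names neither score |
| Logistic regression on treatment agreement plus six imaging features | Association of agreement with outcome | No; no severity score is named |
| LASSO on structural, pathological and intervention variables | Which factors carry weight | No; it ranks factors |
| Calibration curves, precision–recall curves, Brier score | The model's own performance | No reference predictor |
| Interpretability of imaging and clinical features | Contributions inside the model | No head-to-head comparison |

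SOFA or APACHE II may be among the model's inputs, since the candidate predictors are not listed. Being an input does not make a score a comparator.

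**2. The plan's own sample size.** Sample size estimation allows at most 15 predictors at 10 events each: 15 × 10 = 150 deaths, and 150 / 0.375 = 400. The stated figure is reproduced. It rests on events per variable alone and allows for no comparison with a reference predictor.

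**3. Could a score simply join the planned test?** No. With five runs against five, the smallest two-sided rank-sum p-value is 2 / C(10,5) = 2/252 = 0.008. That test reflects run-to-run variation, not sampling of patients. A fixed score has no run-to-run variation, so a patient-level paired comparison is needed.

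**4. How precise would that comparison be?**

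Inputs from the documents are 55 external cases (Sample Size and Data Partitioning) and 37.5% in-ICU mortality (Sample size estimation). The latter is a proxy for 28-day in-hospital death. Expected deaths are 55 × 0.375 = 20.6, taken as 21 deaths and 34 survivors.

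The documents give no AUCs, so these are assumptions: 0.70 for the bedside score, 0.75 to 0.85 for the model, and correlation r of 0.3 to 0.7 between the two AUC estimates.

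Hanley–McNeil, with Q1 = A/(2 − A) and Q2 = 2A²/(1 + A):

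SE² = [A(1 − A) + (n1 − 1)(Q1 − A²) + (n0 − 1)(Q2 − A²)] / (n1·n0)

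For A = 0.70, n1 = 21, n0 = 34: [0.21 + 20(0.0485) + 33(0.0865)] / 714 = 0.00565, so SE = 0.075. For A = 0.80, SE = 0.065.

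Paired difference: SE_d = √(s0² + s1² − 2·r·s0·s1). For 0.70 versus 0.80 at r = 0.5 this is 0.071, and the 95% half-width is 1.96 × 0.071 = 0.139.

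| Model AUC (score 0.70) | Half-width, r = 0.3 / 0.5 / 0.7 | Power, r = 0.3 / 0.5 / 0.7 |
|---|---|---|
| 0.75 | 0.169 / 0.143 / 0.111 | 8% / 10% / 14% |
| 0.80 | 0.164 / 0.139 / 0.108 | 22% / 29% / 44% |
| 0.85 | 0.157 / 0.134 / 0.106 | 47% / 60% / 79% |

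The half-width is thus about 0.11 to 0.17, and the difference detectable with 80% power (2.80 × SE_d) about 0.15 to 0.24. With out-of-sample predictions for all 400 patients (150 deaths), the half-width under the same assumptions would be about 0.04 to 0.06.

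**The case against.** The strongest reply is that this is a development study. Its objectives are to build a model and examine its generalizability and the effects of centre and scanner; none promises superiority over bedside scores. That is true, and it is why the point is a recommended addition and not a flaw that defeats the study. The stated aim of clinical use still makes the missing estimate matter.

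Four stronger readings are tempting, and the documents do not support them.

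- **That the study is unable to show added value.** The scores are collected. The analysis is unplanned, not impossible.
- **That the gap covers severity classification.** The clinical class is the reference standard there, so the model can agree with it but cannot beat it. The point concerns mortality.
- **That bedside information is excluded from the baselines.** The Introduction counts logistic regression on clinical data among machine-learning techniques, so an unnamed baseline could be one. But nothing commits to it.
- **That the baselines will be given fewer inputs.** A reader might infer this from the Introduction's remark "This fragmented view of patient information compromises predictive accuracy in certain cases", but that sentence describes existing methods, not this study's baselines. All that stands is that the plan is silent on input parity.

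It can also be said that 55 external patients cannot settle the comparison. As a hypothesis test that is largely right, given the power figures. It is a reason to report an interval, not to leave the estimate out.

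**Conclusion.** The point holds for 28-day in-hospital mortality. The plan commits to no comparison with SOFA, APACHE II, PaO2/FiO2 or the clinical severity class, and to no test of what the model adds to them. Its sequential-addition analysis runs in the opposite direction. That follows from the text and needs no assumption.

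How much the model gains or fails to gain over bedside data cannot be derived from the documents, and nothing here implies that it adds nothing. What can be sized is the precision of the missing comparison: a half-width of roughly 0.11 to 0.17 on the AUC difference in the external set. This rests on the assumed AUCs and correlations, on in-ICU mortality standing in for the 28-day endpoint, and on the external set being the 55 cases in Sample Size and Data Partitioning.

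**What to change.** In Secondary Outcome Measures and the Statistical Analysis Plan:

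1. Prespecify logistic comparators for 28-day in-hospital mortality using (i) APACHE II, (ii) SOFA, and (iii) the reference severity class or continuous PaO2/FiO2.
2. For each, add a model combining that comparator with the CT model's prediction, so that added value is estimated directly. Use out-of-fold CT predictions when fitting these, because in-sample predictions from a deep model are optimistic.
3. Fit on the development data and score on the same external patients as the proposed model, with one prespecified prediction per patient (for example, the mean over the five runs).
4. Report patient-level paired differences in AUC and Brier score with bootstrap 95% confidence intervals, not the five-run Wilcoxon test. Present them as estimates, with no pass/fail threshold.
5. Name the AI baselines and give them the same inputs and split as the proposed model, or label those with fewer inputs as ablations.

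Out-of-sample predictions across all 400 cases could be added for a tighter interval, but would not be external evidence.

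The cost is a few logistic fits on data already collected and some SAP wording. The reported improvement may turn out smaller than against AI baselines alone, or too imprecise to interpret firmly.

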Advances in AI-enabled deep learning for CT image analysis allow automated identification of parenchymal lung changes, quantitative segmentation of hypo-ventilated or high-density regions, and integration with clinical data to build predictive models. Incorporating multicentre data can improve model generalizability and address the performance decline often observed in external validation of single-centre studies, thereby supporting the development of robust and reliable intelligent auxiliary strategies for ARDS diagnosis and management. Indeed, the high mortality associated with ARDS stems not only from inadequate management strategies but also from challenges in early detection, risk stratification, and severity prediction. Consequently, developing AI-assisted diagnostic and management tools represents a pressing need, particularly for critical conditions such as ARDS [29–31].

Therefore, this study proposes a multicentre retrospective investigation integrating data from 400 ARDS cases across three tertiary comprehensive hospitals. Through standardized image preprocessing and rigorous modeling approaches, we aim to develop and validate a CT-imaging-driven model for ARDS grading and clinical decision support, assess its cross-centre stability, and ultimately provide a generalizable intelligent tool for clinical practice.

Primary Objective

To develop an intelligent assessment model for ARDS severity using multicentre chest CT data. By integrating quantitative CT features with clinical characteristics, the

model aims to predict short-term major clinical events (such as decisions regarding mechanical ventilation, prone positioning strategy, mortality, and ECMO use), stage and quantify the disease, and establish a diagnostic and risk-stratification model for ARDS to assist in guiding therapeutic strategies.

Secondary Objective

To validate the generalizability of the model across external centres and evaluate its applicability in multicentre real-world settings; and to analyze the influence of different centres and CT scanner models on imaging features and model performance.

The overall research design and plan

This was a retrospective, multicenter, observational cohort study.

Study population

This study planned to enroll a total of 400 ARDS patients admitted to the intensive care units of three comprehensive tertiary hospitals.

Inclusion Criteria

1. Patients meeting the **2023 global updated definition of ARDS**.

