Chest CT images for all enrolled cases were exported from the hospital Picture Archiving and Communication System (PACS) in DICOM format. To minimize inter-scanner variability, all non-contrast CT images underwent standardized preprocessing. Using Python (version 3.9.13) and the open-source SimpleITK library (version 2.2.1), all images were converted to NIFTI format. Subsequently, each image was normalized to arrays with a uniform mean and standard deviation to reduce distributional differences across scanners. Following preprocessing, the images were fed into the deep learning (DL) model.

For dataset partitioning, the “createDataPartition” function from the *caret* package was used to perform stratified random sampling, assigning 60% of the data to the training set, 20% to the validation set, and the remaining 20% to the test set. The training set was used to fit the machine learning model, the validation set to select the best-performing model, and the test set to evaluate the final model performance.

Construction of a Deep-Learning Lung Segmentation Model

This study focuses on chest CT images with the lung as the organ of interest; therefore, the lung will be defined as the region of interest (ROI) for the deep-learning (DL) model. We plan to develop a U-shaped Transformer-based model for lung segmentation, with target classes including lesion regions, the whole lung, individual lobes, and all bronchopulmonary segments.

The U-Net architecture is widely used for medical image segmentation and comprises an encoder, a decoder, and skip connections. The encoder extracts local image features through successive convolutional operations and employs down-sampling to progressively expand the network receptive field. Conversely, the decoder upsamples processed features back to the original image resolution to enable pixel-level semantic inference. Skip connections fuse features from corresponding encoder and decoder layers, ensuring comprehensive feature maps that preserve precise spatial information alongside high-level semantics, which is critical for accurate segmentation. A Transformer can serve as the backbone within the U-Net encoder/decoder blocks; by using global attention mechanisms, it captures long-range dependencies and, in principle, attains a global receptive field.

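### The 60/20/20 random split in the image-processing section contradicts the held-out-centre design and could put external test cases into training

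*Combined protocol and SAP*

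**What the plan says.** Three places in the combined protocol and SAP describe how cases are divided.

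- **Sample Size and Data Partitioning.** The development data come from two centres: "Training set: 276 cases (approximately 80% of the combined cases from the primary institution and Sub-center 2"). A further 69 cases from the same two centres form the internal validation set, used to watch for overfitting and to tune hyperparameters. The third centre is held out: "External test set: 55 cases, all derived from Sub-center 1 and entirely independent of the model development process".
- **Statistical Analysis Plan.** Cases are "stratified and randomly sampled at an 8:2 ratio within Shanghai General Hospital and its affiliated centers" to form the training and internal validation sets, and "Cases from an additional participating center will be reserved as an independent external test cohort". No counts are given.
- **Research procedures, 3. Quantitative Assessment of ARDS, Preliminary Image Processing.** The section opens with "Chest CT images for all enrolled cases were exported from the hospital Picture Archiving and Communication System". It then describes a stratified random split, "assigning 60% of the data to the training set, 20% to the validation set, and the remaining 20% to the test set". The validation set selects the best model, and the role of the last part is "the test set to evaluate the final model performance". No centre is named and no held-out centre is mentioned.

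The Secondary Objective begins "To validate the generalizability of the model across external centres".

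**The concern.** The first two places describe a held-out-centre design. The third describes a random split in which centre plays no stated part. The split sentence does not name the population it applies to, so it can be read in two ways.

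- **Reading A: all 400 cases.** This follows from the section's opening. Sub-center 1 cases then enter training and model selection, which contradicts their stated independence, and the test set is no longer external.
- **Reading B: only the 345 development-centre cases.** Sub-center 1 stays unseen, but the set sizes change and a second test set exists that no other section describes.

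External generalizability is a stated objective, and Sub-center 1 is the only centre reserved for it. The three primary outcomes name no dataset, while the image-processing section assigns final performance to its own test set. A reader therefore cannot tell which test set the main results will come from, and the choice could be made after results are seen.

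**Working it through.** **Inputs.** Total 400; training 276; internal validation 69; external test 55, all Sub-center 1; 300 cases from the primary institution and Sub-center 1 together; 100 from Sub-center 2 (all from Sample Size and Data Partitioning). Split fractions 0.60/0.20/0.20 (Preliminary Image Processing).

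**1. Reproduce the plan's own partition.**
- Primary institution: 300 − 55 = 245. Development pool: 245 + 100 = 345.
- 0.8 × 345 = 276; 0.2 × 345 = 69; 276 + 69 + 55 = 400.

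The partitioning section is exact. As shares of 400 it is 69.0% / 17.25% / 13.75%, not 60/20/20.

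**2. Reading A (all 400).**
- Set sizes: 0.6 × 400 = 240; 0.2 × 400 = 80; remaining 80.
- Expected Sub-center 1 cases: training 240 × 55/400 = 33; validation 80 × 55/400 = 11; test 11.
- Spread, treating placement as hypergeometric with N = 400 and K = 55: variance = n(K/N)(1 − K/N)(N − n)/(N − 1).
  - Training, n = 240: 240 × 0.1375 × 0.8625 × 160/399 = 11.41, SD 3.38, 95% range 26 to 40.
  - Test, n = 80: 80 × 0.1375 × 0.8625 × 320/399 = 7.61, SD 2.76, 95% range 6 to 17.
- Development-centre share of the test set: (80 − 11)/80 = 69/80 = 86%.
- External cases that stay unseen fall from 55 to about 11.

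This assumes that the stratification variable is unrelated to centre.

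**3. Reading B (345 only).**
- Set sizes: 0.6 × 345 = 207; 0.2 × 345 = 69; remaining 69.
- Sub-center 1 cases in training: 0.
- Training set against the stated 276: 1 − 207/276 = 25% smaller.

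**4. Side by side.**

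| Scheme | Training | Validation | Test | Sub-center 1 cases in training |
|---|---|---|---|---|
| Partitioning section | 276 | 69 | 55 (external) | 0 |
| 60/20/20 of 400 | 240 | 80 | 80 (mixed centres) | about 33 |
| 60/20/20 of 345 | 207 | 69 | 69 (internal) | 0 |

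Neither reading of the 60/20/20 sentence returns the stated partition.

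**The case against.** The strongest reply is that the section dedicated to partitioning and the SAP both hold out a centre, and that a generic sentence under image preprocessing should not be taken to override them. Leakage is possible but not shown, and under Reading B it is zero. That is right: the figure of 33 is conditional, and the certain defect is the unreconciled partition.

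There is also a near match that favours Reading B. Within the 345 cases, 207 + 69 = 276 and the last 69 equals the internal validation count. The roles still clash: the partitioning section tunes hyperparameters on its 69 cases, while the image-processing section keeps its last 20% for final evaluation. One set cannot serve both purposes without biasing the evaluation.

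The scope of the sentence is less clear than its opening suggests. It refers to a single hospital's image archive, and to a machine learning model and an R package within an otherwise Python deep-learning pipeline, so it may concern another component. Nothing in the text says so, and the ambiguity would remain.

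The past tense of the split sentence is weak evidence that the split was run, because the document mixes tenses throughout. It justifies asking the sponsor, no more. Finally, the SAP supports the 8:2 structure and the held-out centre but not the counts of 276, 69 and 55.

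**Conclusion.** The inconsistency holds under either reading and must be fixed. The held-out-centre design is sound; the fault lies in the one sentence that departs from it. If the split covers all 400 cases, about 33 of the 55 external cases are expected in training and another 11 in validation, so the external test is lost. If it covers only the 345, the external test survives, but the set sizes and the number of test sets contradict the partitioning section. The documents do not settle which reading applies or whether either split has been run.

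A related gap prevents the SAP from resolving this. It defines the development pool by a hospital name and its affiliated centres, whereas the partitioning section uses the primary institution and Sub-center 2. The available text does not show that these are the same centres.

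**What to change.** 1. Confirm and state which split was actually run, and on which centres.
2. Delete the 60/20/20 sentence or replace it with the partitioning section's rule: the 345 primary-institution and Sub-center 2 cases are split 276/69, stratified by severity; all 55 Sub-center 1 cases are excluded from every development step, including segmentation training, feature selection and tuning, and are used only for final evaluation.
3. State which dataset each primary outcome is reported on.
4. If a random split over all centres was already run, report that and refit with Sub-center 1 excluded.
5. Have the sponsor confirm which centres the SAP's hospital name covers, and use the same centre labels in the partitioning section and the SAP.

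**Cost.** If no cross-centre split was run, this is a change of wording in the protocol and SAP. If one was run, the models must be refitted. No new patients are needed in either case. Performance on a truly held-out centre may look less favourable than on a mixed-centre test set.
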